**Sample Size Estimate:**

Initially, cohorts of approximately 10 subjects will be enrolled sequentially at progressively shorter infusion durations, beginning with the 60-minute infusion duration, progressing down to the 45-minute infusion duration and then to the 30-minute infusion duration.

Approximately 110 subjects are planned to be enrolled into the selected cohort. Therefore, the minimum number of subjects enrolling across the 3 different cohorts in the study is approximately 130.

Based on the MIRROR-RCT study (NCT03994731), approximately 5.0% of subjects are expected to have an IR (including events of anaphylaxis) when taking pegloticase concurrently with MTX. The sample size of 110 for the selected cohort is chosen to ensure a high probability of ruling out an unacceptably high IR rate. If the observed IR rate is 5%, there is a greater than 80% probability that the upper bound of the two-sided 95% exact confidence interval for the IR rate is less than 13%.

## 2.1 Schedule of Assessments

Study Procedure/ Assessment	Screening	MTX Tolerability Assessment Period/ Run-in Period 		Pegloticase + MTX Period  Day 1 through Week 24											End-of- Pegloticase- Infusions Visit  (if applicable)	End-of- study/ Early Term.	Safety Follow-up	Post Treatment Follow- Up 
	Screening Visit  (35 d)	Week - 4 (±3 d)	Week - 2 (±3 d)	Week (±3 d)											Within 2 weeks following final infusion if prior to Wk 22	Wk 24 (±3 d)	30 days after last pegloticase infusion (±3 d)	3 Months
				Day 1	2	4	6	8	10	12	14	16	18	20	22			
Pegloticase infusion				Inf 1	Inf 2	Inf 3	Inf 4	Inf 5	Inf 6	Inf 7	Inf 8	Inf 9	Inf 10	Inf 11	Inf 12			
Informed consent	X																	
Enrollment				X														
Demographic data	X																	
Inclusion/ exclusion criteria	X	X		X														
Medical/Surgical History 	X																	

Study Procedure/ Assessment	Screening	MTX Tolerability Assessment Period/ Run-in Period 		Pegloticase + MTX Period  Day 1 through Week 24											End-of- Pegloticase- Infusions Visit  (if applicable)	End-of- study/ Early Term.	Safety Follow-up	Post Treatment Follow- Up 
	Screening Visit  (35 d)	Week - 4 (±3 d)	Week - 2 (±3 d)	Week (±3 d)											Within 2 weeks following final infusion if prior to Wk 22	Wk 24 (±3 d)	30 days after last pegloticase infusion (±3 d)	3 Months
	Day 1	2	4	6	8	10	12	14	16	18	20	22						
Medication/substance use history 	X																	
Physical examination 	X	X	X	X	X	X	X	X	X	X	X	X	X	X	X	X	X	X
Vital signs, height and weight 	X	X	X	X	X	X	X	X	X	X	X	X	X	X	X	X		X
Electrocardiogram 	X																	
AE/SAE Assessment 	X	X	X	X	X	X	X	X	X	X	X	X	X	X	X	X	X	X
Concomitant medications 	X	X	X	X	X	X	X	X	X	X	X	X	X	X	X	X		X
Principle Investigator Assessment of gout flares and intensity	X	X	X	X	X	X	X	X	X	X	X	X	X	X	X	X	X	X

Study Procedure/ Assessment	Screening	Pegloticase + MTX Period  Day 1 through Week 24												End-of-Pegloticase-Infusions Visit  (if applicable)	End-of-study/ Early Term.	Safety Follow-up	Post Treatment Follow-Up 		
	Screening Visit  (35 d)	Week - 4 (±3 d)	Week - 2 (±3 d)	Week (±3 d)												Within 2 weeks following final infusion if prior to Wk 22	Wk 24 (±3 d)	30 days after last pegloticase infusion (±3 d)	3 Months
	Day 1	2	4	6	8	10	12	14	16	18	20	22							
MTX dosing calendar		X	X	X	X	X	X	X	X	X	X	X							
MTX dispensed 		X	X	X	X	X	X	X	X	X	X	X							
MTX dosing 		Once weekly from Week -4 to Week 23, one week after the Week 22 Visit, inclusive																	
Gout prophylaxis Rxs filled 		Rxs filled as needed, start taking at least one protocol standard gout flare prophylaxis regimen ≥1 week before first dose of pegloticase.																	
Fexofenadine Rx filled 			Rxs filled as needed, first dose of fexofenadine must be taken the day before D1; and in the morning or just prior to each infusion.																
Folic Acid Rx filled 		Rxs filled as needed, 1 mg orally every day beginning at Week -4.																	

Study Procedure/ Assessment	Screening	MTX Tolerability Assessment Period/ Run-in Period 		Pegloticase + MTX Period  Day 1 through Week 24											End-of- Pegloticase- Infusions Visit  (if applicable)	End-of- study/ Early Term.	Safety Follow-up	Post Treatment Follow- Up 
	Screening Visit  (35 d)	Week - 4 (±3 d)	Week - 2 (±3 d)	Week (±3 d)											Within 2 weeks following final infusion if prior to Wk 22	Wk 24 (±3 d)	30 days after last pegloticase infusion (±3 d)	3 Months
	Day 1	2	4	6	8	10	12	14	16	18	20	22						
IR prophylaxis 				X	X	X	X	X	X	X	X	X						
IR Rx prophylaxis compliance check (Yes/No)				X	X	X	X	X	X	X	X	X						
Gout flare prophylaxis compliance check (Yes/No)		X		X	X	X	X	X	X	X	X	X						
Pre-infusion MTX Polyglutamate sampling				X									X	X	X	X		
Pegloticase PK sampling 				X	X		X						X		X			
sUA 	X	X	X	X	X	X	X	X	X	X	X	X	X	X	X	X	X	
Hematology 	X 		X	X	X		X			X			X	X	X		X	

Study Procedure/ Assessment	Screening	MTX Tolerability Assessment Period/ Run-in Period 		Pegloticase + MTX Period  Day 1 through Week 24											End-of- Pegloticase- Infusions Visit  (if applicable)	End-of- study/ Early Term.	Safety Follow-up	Post Treatment Follow- Up 
	Screening Visit  (35 d)	Week - 4 (±3 d)	Week - 2 (±3 d)	Week (±3 d)											Within 2 weeks following final infusion if prior to Wk 22	Wk 24 (±3 d)	30 days after last pegloticase infusion (±3 d)	3 Months
	Day 1	2	4	6	8	10	12	14	16	18	20	22						
Chemistry	X		X	X	X		X			X			X	X	X		X	
Urine Albumin: Creatinine Ratio 	X			X	X		X			X			X	X	X			
Antibody testing 				X	X		X			X			X		X		X	
C-Reactive Protein				X						X					X			
G6PD	X																	
Serum Pregnancy Test 	X														X			
Urine Pregnancy test 		X	X	X	X	X	X	X	X	X	X	X				X		
Partner pregnancy 																		X

**Abbreviations:** AE = adverse event; d = day(s); G6PD = glucose-6-phosphate dehydrogenase; IR = infusion reaction; PK = pharmacokinetic; Rx = prescription; SAE = serious adverse event; sUA = serum uric acid; UACR= Urinary Albumin Creatinine Ratio; V = Visit; wk(s) = week(s)

Footnotes:

1. The Screening Visit can occur up to 35 days prior to Week -4 visit HbA1c testing is required as part of the Hematology panel during Screening period (refer to Guidance on Blood Glucose Monitoring in Section 9.1).
2. During the MTX Tolerability Assessment Period (starting at Week -4 to Day 1), all subjects will take MTX 15 mg orally weekly. The subject must tolerate MTX 15 mg dose during MTX Run in Period to enroll into the Pegloticase + MTX Period. If a subject does not tolerate the MTX 15 mg dose during the Pegloticase + MTX Period, MTX may be dose-reduced after discussion with the Sponsor medical monitor. The subject should remain in the study.
3. Subjects who end treatment due to the sUA Discontinuation Criteria or other reasons should complete the End of Pegloticase Infusions Visit within 2 weeks of the last infusion. Subjects will also complete all regularly scheduled Follow-Up visits including the 30-day Follow-up email/phone call, Week 24/End of Study/Early Termination and 3 Month Post-Treatment Follow-up Visits.
4. Subjects will be enrolled at the Day 1 Visit to receive pegloticase 8 mg administered IV every 2 weeks from Day 1 through Week 22, inclusive. During this 24-week treatment phase, subjects who meet the Individual Subject sUA Discontinuation Criteria or discontinue treatment for any other reason will enter the off-treatment observation period. During the off-treatment observation period, subjects will return for scheduled visits according to [section 9.4.3](#).
5. The Investigator or designee will collect a complete gout history and other relevant medical/surgical history.
6. Medication history (i.e., prior medications) will include gout medications, starting at the time of diagnosis and up to (but not including) the Day 1 Visit; substance use history; and all other medications up to (but not including) the Day 1 Visit. Prior concomitant medications (not including gout medications) will be collected for 1 year prior to screening (as well as history of COVID-19 vaccinations).
7. A complete physical examination will be performed at the Screening Visit, including assessment of HEENT, heart, lungs, abdomen, skin, extremities and neurological status and musculoskeletal including an assessment for the presence of tophi, as well as gout history and symptom severity. Physical examination findings at screening should be recorded on the medical and surgical history eCRF. A targeted physical examination (for assessment of AEs) will be conducted based on potential risk for or occurrence of AEs at Week -4, Week -2, Day 1 and prior to administration of infusion at Weeks 4, 8, 12, 16, 20, End of Pegloticase Infusions Visit (if applicable), 24/End of Study/Early Termination Visits and 3-Month Follow-Up. Clinically significant findings from the targeted physical examinations will be recorded as AEs.
8. Routine vital signs, including BP, respiratory rate, temperature and heart rate will be measured at Screening, Week -4, Week -2 and at all infusion visits during the Pegloticase + MTX Period and the End of Pegloticase Infusions Visit (if applicable), Week 24/End of Study/Early Termination and 3-month Post-Treatment Follow-up Visit. Heart rate and BP measurements should be taken after the subject has been in a sitting position and in a rested and calm state with proper positioning including back support, feet flat on the floor, for at least 5 minutes. Subjects arm should be supported at heart level; and cuff placed on the bare arm. A large cuff should be used as needed to fit the upper arm and a consistent arm is to be used at each study visit. The Korotkoff phase V will be used to determine

diastolic BP. During the Pegloticase + MTX Period study visits, vitals should be taken before the pegloticase infusion and any time after the end of the infusion, but prior to subject's discharge/release from the site. When possible, the same staff member should take all BP measurements for a given subject. Weight should be measured in kilograms or pounds without shoes and recorded at the Screening Visit and prior to dosing MTX Week -4 Visit; prior to pegloticase infusion on Day 1 and at the Weeks 8, 16 and at the non-infusion End of Pegloticase Infusions Visit (if applicable), Week 24/End of Study/Early Termination and Month 3 Post-Treatment Follow-up Visits. Height will be collected at the Screening Visit only.

9. Electrocardiogram should be completed at Screening Visit, during the study per investigator discretion and during any potential or suspected IR.
10. AEs/SAEs will be collected from the signature of the ICF through the 3-month Post-Treatment Follow-up visit.
11. MTX tablets will be dispensed and brought back at each visit to check compliance. MTX bottles are 36 count and bottles should be re-dispensed when appropriate. New bottles should not be given at each visit. If subjects require a MTX dose reduction, the Investigator will prescribe the subject the number of tablets to take weekly. The updated number of tablets along with the date and time of each MTX dose should be recorded in the dosing calendar.
12. 15mg of MTX should be taken 1 to 3 days prior to pegloticase infusion; however, if a subject does not do so, MTX must be taken  $\geq$ 60 minutes prior to pegloticase infusion.
13. It is required that before a subject begins the pegloticase + MTX Period, he or she has been taking at least one protocol standard gout flare prophylaxis regimen (i.e. colchicine and/or non-steroidal anti-inflammatory drugs and/or low dose prednisone  $<10$  mg/day) for  $\geq$ 1 week before the first dose of pegloticase and continuing throughout the pegloticase treatment period per American College of Rheumatology guidelines [Khanna D et al. 2012].
14. Fexofenadine (180 mg orally) will be taken the day before and the morning or just prior to each infusion. Prescriptions are to be filled at a local pharmacy, as needed.
15. Subjects will take folic acid 1 mg orally every day beginning at Week -4 (the start of MTX) until prior to the End of Pegloticase Infusions Visit (if applicable) or the Week 24/End of Study/Early Termination. Prescriptions are to be filled at a local pharmacy, as needed.
16. IR prophylaxis: fexofenadine (180 mg orally) administered the day before each infusion; fexofenadine (180 mg orally) and acetaminophen (1000 mg orally) administered on the morning of each infusion; and methylprednisolone (125 mg IV) will be administered over an infusion duration between 10 – 30 minutes, immediately prior to each pegloticase infusion.
17. For all subjects, serum samples for pegloticase PK analysis will be collected approximately 15 minutes to 2 hours after the end of infusion on Day 1; prior to infusion and approximately 15 minutes to 2 hours after the end of infusion at the Weeks 2, 6, 12, 20. An additional PK sample will be collected at Week 24 End of Study/Early Termination Visits.
18. Serum samples for measurement of sUA levels will be collected at the Screening Visit, the Week -4 Visit and the Week -2 Visit during the Run-in Period; within 48 hours prior to each pegloticase infusion and after the end of each pegloticase infusion prior to discharge from the site during the Pegloticase + MTX Period on Day 1, at the Weeks 2, 6, 10, 12, 14, 20 and 22; within 48 hours prior to each pegloticase infusion at Weeks 4, 8, 16, 18. Additional serum samples for sUA levels will be collected at non-infusion Visits at the End of Pegloticase Infusions Visit (if applicable) and the Week 24/End of study/Early Termination Visit and 3-

month Follow-up Visit. A subject with sUA level  $>6$  mg/dL (based on the local or central laboratory) at 2 consecutive study visits, beginning with the Week 2 Visit, will be discontinued from pegloticase treatment and remain on study. If a subject's previous visit pre-infusion sUA was  $<6$  mg/dL – sUA result is not required for the following infusion visit (local pre-infusion sUA may be drawn at the same time as central pre-infusion sample). If a subject's previous visit pre-infusion sUA was  $>6$  mg/dL – local sUA is required to be resulted (within 48 hours) to confirm stopping criteria was not met. See Section 9.6.2.1 and the Laboratory Manual for instructions for alternate scenarios. In the event of an AE suspected to be an IR, a serum sample will be collected at that time or at the subsequent visit for evaluation of pegloticase antibodies.

19. Serum samples for evaluation of anti-PEG antibodies and anti-uricase IgG antibodies will be collected prior to the infusion on Day 1 and at the Weeks 2, 6, 12, 20. An additional sample will be collected at each of the End of Study/Early Termination Visit and the 3-month Study Follow-up Visit. In the event of an AE suspected to be an IR, a serum sample will be collected in a SST tube at that time or at the subsequent visit for evaluation of anti-drug antibodies.
20. For women of childbearing potential, a serum pregnancy test will be performed at the Screening Visit; at the End-of-Study/Early Termination Visit.
21. For women of childbearing potential, a urine pregnancy test will be performed at all indicated visits and results must be confirmed by site personnel prior to any infusion starting. If the subject has not ovulated by the 30-day Follow-up email/phone call, the subject will be requested to return to the site for a urine pregnancy test.
22. Urine Albumin: Creatinine Ratio is derived data by the lab using results from urine.
23. The intent is to obtain at least 3 months of follow-up on each subject after cessation of pegloticase infusions. If the subject ends treatment early but remains in the study and the 3-month Post-Treatment Follow-up Visit occurs prior to Week 24, the 3-month Post-Treatment Follow-up Visit will be adjusted accordingly based on the timing of the last treatment. All subjects will be followed for a minimum of 3 months following Week 24/End-of-Study/Early Termination Visit.
24. Subjects who are non-vasectomized males will be asked 3 months after MTX discontinuation regarding partner pregnancy. This will occur at a regularly scheduled visit or by a separate phone/email visit.
25. Thirty (30) days after the last MTX dose, subjects will be contacted by telephone or email to review AEs and SAEs. Subjects who are females of childbearing potential will be asked to confirm that ovulation has occurred. If the subject has not ovulated, the subject will be requested to return to the site for a urine pregnancy test.

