**Week 24/End of Study/Early Termination Visit.**

Subjects must be able to tolerate MTX at a dose of 15 mg during the 4-week MTX Run-in Period (prior to Day 1) to be eligible to participate in the Pegloticase + MTX Period.

Subjects who are unable to tolerate MTX at a dose of 15 mg during the MTX Run-in Period will be considered screen failures.

Female subjects who take at least one dose of MTX and who are females of childbearing potential, will receive a safety Follow-up phone call/e-mail approximately 30 days after the last dose of MTX to verify at least one ovulatory cycle has occurred after the last dose of MTX. If the subject has not ovulated, a urine pregnancy test will be performed. For those subjects who take at least one dose of MTX and who are non-vasectomized males an inquiry will be conducted at the Post-Treatment 3-month Follow-up visit (or 3 months after the subject's last dose of MTX) after MTX discontinuation regarding partner pregnancy.

All subjects who complete the Run-In Period and meet the inclusion/exclusion criteria will receive the first pegloticase infusion on Day 1. All subsequent doses and study visits will be scheduled based on the Day 1 visit date.

Prior to the Treatment Period, subjects will begin taking at least one of the per protocol standard gout flare prophylaxis regimen (colchicine 0.6 mg/day and/or nonsteroidal anti-inflammatory drug (NSAID) and/or low dose prednisone <10 mg/day) for  $\geq 1$  week before the first dose of pegloticase and continues flare prophylaxis throughout the pegloticase treatment period per American College of Rheumatology guidelines [Khanna D et al. 2012].

For IR prophylaxis, fexofenadine (180 mg orally) will be taken the night before each infusion; fexofenadine (180 mg orally) and acetaminophen (1000 mg orally) will be taken the morning of each infusion; and methylprednisolone (125 mg IV) over an infusion duration between 10 and 30 minutes, will be administered immediately prior to each infusion.

During the Pegloticase + MTX Period, all subjects will receive pegloticase 8 mg every 2 weeks administered IV for a total of 12 infusions from Day 1 through Week 22, inclusive.

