### **Guidance on Blood Glucose Monitoring:**

HbA1c testing must be performed at Screening for all subjects (locally or centrally): If HbA1c >6.5% and/or if subject has known diagnosis of diabetes mellitus, additional measures are recommended:

- Investigator asked to closely monitor glucose levels and adjust any diabetic medications as necessary
- Subject should consult their primary care physician and/or Endocrinologist managing their diabetes

The pre-infusion IV steroid dose may be reduced (e.g., methylprednisolone 75 mg IV) after consulting with the Horizon Medical Monitor.

All subjects who meet eligibility criteria at Screening will begin oral MTX at a dose of 15 mg weekly for 4 weeks prior to the first dose of pegloticase.

Subjects will also take folic acid 1 mg orally every day beginning at Week -4 (the start of MTX) continuing until prior to the End of Pegloticase Infusion Visit (if applicable) or the Week 24/End of Study/Early Termination Visit. Subjects must be able to tolerate MTX at a dose of 15 mg during the 4-week MTX Run-in Period (prior to Day 1) to be eligible to participate in the Pegloticase + MTX Period. Subjects who are unable to tolerate MTX at a dose of 15 mg during the MTX Run-in Period will be considered screen failures and not proceed to pegloticase dosing.

Female subjects who take at least one dose of MTX and who are of childbearing potential, will receive a safety Follow-up phone call/e-mail approximately 30 days after the last dose of MTX to verify at least one ovulatory cycle has occurred after the last dose of MTX. If the subject has not ovulated, a urine pregnancy test will be performed. For male subjects who take at least one dose of MTX and who are non-vasectomized an inquiry will be conducted at the Post-Treatment 3-month Follow-up visit (or 3 months after the subject's last dose of MTX) after MTX discontinuation regarding partner pregnancy.

All subjects who complete the Run-In Period and meet the inclusion/exclusion criteria will receive the first pegloticase infusion on Day 1. All subsequent doses and study visits will be scheduled based on the Day 1 visit date.

It is required that before a subject begins the Pegloticase + MTX Period, he or she has been taking at least one protocol standard gout flare prophylaxis regimen (i.e. colchicine and/or

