##### **9.4.3.1.1 Study considerations for subjects ending pegloticase infusions prior to 24 weeks**

- Methotrexate, along with folic acid, will be discontinued at the time of cessation of pegloticase infusions prior to Week 24.
- All subjects will complete the End of Pegloticase Infusions Visit and should be encouraged to remain on study and attend all Follow-Up visits, including the 30-day Follow-up Email/Phone call, Week 24/End of Study/Early Termination and 3 Month Post-Treatment Follow-up Visits barring withdrawal of consent from study participation.
- Activities related to pre/post infusion monitoring or medication dispensation will not be completed once a subject has stopped pegloticase infusions. These activities include:
  - MTX compliance/reconciliation

- IR prophylaxis
- IR prophylaxis compliance
- Folic acid compliance
- Pegloticase infusion
- Pegloticase PK sampling
- Pre-infusion MTX Polyglutamate sampling
- MTX drug/dispensation related items

Post-Treatment Follow-up:

The intent is to obtain at least 3 months of follow up on each subject after cessation of pegloticase infusions. If the subject ends treatment early but remains in the study and the 3-month Post-Treatment Follow-up Visit occurs prior to Week 24, the 3-month Post-Treatment Follow-up Visit will be adjusted accordingly based on the timing of the last treatment.

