Time to event to each individual component of the composite endpoint will also be summarized descriptively. To account for the competing events nature of these events, the cumulative incidence function will be determined and estimates of the cumulative incidence by Week 24 and median time to event for each event will be summarized with a 95% CI for the median time (if available). Subjects who do not experience any of the competing events or the event of interest will be censored at the date of their last infusion.

A competing event is defined as any of the components of the composite endpoint or discontinuation from treatment for any reason. Other competing events may be included in the analysis, as needed.

The time to an event will be calculated by date of event – date of first dose of treatment + 1. Patients who do not experience an event will be censored at time given by date of last dose of treatment - date of the first dose of the treatment + 1.

Events of anaphylaxis and IRs are collected as “reported events” and “adjudicated events”. For all relevant endpoints, separate analyses will be created for reported events and adjudicated events.

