### 3.4.3 Exploratory Endpoint Analyses

## 3.5 Analysis of Pegloticase Pharmacokinetics, Methotrexate Polyglutamates, and Anti-Drug Antibodies

### 3.5.1 Pegloticase and MTX PK

Serum samples for pegloticase PK analysis will be collected approximately 15 minutes to 2 hours after the end of infusion on Day 1; prior to infusion and approximately 15 minutes to 2 hours after the end of the infusion at Weeks 2, 6, 12 and 20. An additional PK sample will be collected at the End-of-Study (Week 24)/Early Termination Visit.

PK summaries will be done for the PK analysis set. MTX polyglutamate summaries will be done for the mITT analysis set. All results will be presented by 'as assigned' infusion duration group.

The following presentations of subject serum pegloticase concentration data covered in this SAP will be provided for pegloticase:

- A listing including subject, week/time point (actual, planned), treatment and serum concentrations. End of infusion sampling times are expressed relative to the start time of infusion.
- A table summary of serum pegloticase concentrations at each time point (n; mean, SD, coefficient of variation (CV)% calculated as  $100\% \times SD/mean$ , minimum, 25th percentile, median, 75th percentile, maximum, geometric mean and geometric CV%) will be provided for the PK analysis set. Similar tables will be produced by Month 6 sUA responder status.

Further, the mean and CV% of pegloticase concentrations will be provided by visit in the subset of subjects who are ADA positive (defined as positive for anti-PEG or anti-uricase antibodies at any visit) and ADA negative (defined as negative for both anti-PEG and anti-uricase antibodies at all visits) for each visit.

All concentrations BLQ after the first pegloticase infusion will be imputed by half of LLOQ for the analysis summaries. The number of BLQ records will be summarized. Concentrations more than 17 days after the last infusion will be excluded from the summary.

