### 3.6.3.4 AEs of Special Interest

Incidence of IRs, anaphylaxis, gout flares and Major Adverse Cardiovascular Events (MACE) will be summarized for the safety analysis set by infusion duration group. Separate summaries will be produced for adjudicated events and reported events (only applies to IRs, anaphylaxis and MACE events – gout flares are not adjudicated).

Summaries of IRs and anaphylaxis will group events by 3 categories:

- Anaphylaxis
- Infusion reactions including anaphylaxis
- Infusion reactions excluding anaphylaxis

Both the investigator-reported and adjudicated events and the associated signs and symptoms will be summarized separately by severity, and the time relative to the most recent pegloticase infusion for each category above. Signs and symptoms will also be summarized by SOC and PT.

Time relative to the most recent pegloticase infusion will be categorized as: during infusion,  $\leq 2$  hours after infusion,  $> 2$  hours to 24 hours after infusion, and  $> 24$  hours after infusion. If the time of the infusion reaction or anaphylaxis is missing, the category will be assigned as “Missing”.

Serious events and the associated symptoms will be summarized by SOC and PT for each category.

The number of events per subject per treatment infusion duration group, the number of events and serious events per infusion, and the number of subjects with the first event by infusion number will be summarized as well for each category. IRs (including anaphylaxis) that occur on the same date will be considered one event.

In addition, the number and percentage of subjects with adjudicated IRs, including anaphylaxis, will be summarized by severity of event using the following categories for both anti-PEG and anti-uricase antibodies:

- ADA status at baseline (positive or negative)
- ADA status post-baseline (positive or negative)
  - ADA positive post-baseline: negative at baseline and positive at any post-baseline time point, or positive at baseline and with an increase in titer at post-baseline timepoint
  - ADA negative post-baseline: defined as negative at all time points, or positive at baseline and without post-baseline increases in titer from baseline titer

MACEs are defined as: including non-fatal myocardial infarction, non-fatal stroke, cardiovascular death, and congestive heart failure. The following search algorithm will be used to identify possible MACEs:

- For cardiovascular death: any fatal cases with following terms

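### The 17-day PK cut-off in SAP 3.5.1 drops compliant Week 24 samples, which may lie up to 20 days after the Week 22 infusion

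*Protocol*

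**What the plan says.** Dosing is fixed in the protocol synopsis: "all subjects will receive pegloticase 8 mg every 2 weeks administered IV for a total of 12 infusions from Day 1 through Week 22, inclusive". Protocol Section 9.1 anchors the calendar: "All subsequent doses and study visits will be scheduled based on the Day 1 visit date". The Schedule of Assessments gives each visit after Day 1, including Week 24, a window of ±3 days.

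Footnote 17 of Protocol Section 2.1 places PK samples after the Day 1 infusion and then "prior to infusion and approximately 15 minutes to 2 hours after the end of infusion at the Weeks 2, 6, 12, 20". It then adds: "An additional PK sample will be collected at Week 24 End of Study/Early Termination Visits".

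SAP Section 3.5.1 tabulates serum concentrations by time point and assigned infusion duration, with further tables by Month 6 responder status and by ADA status. One sentence limits which samples enter: "Concentrations more than 17 days after the last infusion will be excluded from the summary". The SAP does not explain the 17 days. It does not say whether *last infusion* is the preceding or the final one, or whether the interval is counted in calendar days or by clock time.

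**The concern.** Seventeen days is one dosing interval plus one visit window. That is the longest compliant gap only where the earlier of the two visits has no window of its own, which is true of Day 1 alone. Elsewhere both the infusion visit and the sampling visit can move, in opposite directions, with no deviation. A cut-off of 17 days therefore removes samples that the protocol treats as on schedule.

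The rule also works on one side only. It has no lower limit, so compliant samples taken early stay in. If concentrations decline between infusions, the samples removed tend to be the lower ones and the tabulated mean moves up. At stake is the accuracy of a descriptive PK table, chiefly its Week 24 row. In the initial cohorts of about 10 subjects, one excluded sample is a tenth of the cell.

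**Working it through.** **Inputs.** Infusion interval 14 days and windows of ±3 days (Protocol Section 2.1 and synopsis); anchor Day 1 (Protocol Section 9.1); target days from SAP Table 1; cut-off 17 days (SAP 3.5.1). The documents give neither a half-life nor the spread of actual visit days.

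**1. The plan's figure.** 14 + 3 = 17 days. This matches the cut-off and is the compliant maximum for Week 2.

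**2. Compliant gaps.** Gap = 14 + d(sample visit) − d(infusion visit), with each d from −3 to +3 and d = 0 on Day 1.

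| PK visit | Preceding infusion | Longest gap | Shortest gap |
|---|---|---|---|
| Week 2 | Day 1 | 18 − 1 = 17 | 12 − 1 = 11 |
| Week 6 | Week 4 | 46 − 26 = 20 | 40 − 32 = 8 |
| Week 12 | Week 10 | 88 − 68 = 20 | 82 − 74 = 8 |
| Week 20 | Week 18 | 144 − 124 = 20 | 138 − 130 = 8 |
| Week 24 | Week 22 | 172 − 152 = 20 | 166 − 158 = 8 |

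**3. Which rows the rule can reach.** If *last infusion* is the final one, a pre-infusion sample that is followed by an infusion cannot be excluded, so among scheduled visits the rule bears on Week 24. If it is the preceding one, the pre-infusion samples at Weeks 6, 12 and 20 are exposed too. For a subject dosed at Week 22 the two readings coincide at Week 24. Week 2 is untouched either way in whole days.

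**4. Share excluded at an exposed visit.** A gap above 17 needs d(sample) − d(infusion) of at least 4. Treating the two deviations as independent:

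- Uniform days: (3 + 2 + 1)/49 = 6/49 = 12.2%.
- Triangular weights 1, 2, 3, 4, 3, 2, 1 (sum 16): (10 + 4 + 1)/256 = 5.9%.
- Peaked, 60% on target and 11%, 6% and 3% at 1, 2 and 3 days either side: 0.0102 + 0.0036 + 0.0009 = 1.5%.

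If all 110 subjects were dosed at Week 22 and sampled at Week 24, that is about 13, 6 or 2 samples.

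**5. One-sidedness.** With uniform days the mean compliant gap is 14. After exclusion it is (49 × 14 − 3 × 18 − 2 × 19 − 20)/43 = 574/43 = 13.35 days.

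**6. Effect on the mean.** Assume C(gap) = exp(−ln 2 × (gap − 14)/h), with h the half-life in days. The table gives the retained mean divided by the mean of all compliant samples. For uniform days and h = 7 this is 1.097/1.040 = 1.0548.

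| Visit days | h = 3 | h = 7 | h = 14 | h = 21 |
|---|---|---|---|---|
| Uniform | 1.1005 | 1.0548 | 1.0298 | 1.0204 |
| Triangular | 1.0423 | 1.0229 | 1.0125 | 1.0085 |
| Peaked | 1.0098 | 1.0053 | 1.0029 | 1.0020 |

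**7. Would 20 days still screen out missed infusions?** The shortest in-window gap after one missed infusion is 28 − 3 − 3 = 22 days (for example, Week 24 on Day 166 after Week 20 on Day 144). A 20-day limit lies between 20 and 22 and separates the two groups.

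**The case against.** The strongest reply is that the rule was never aimed at troughs during dosing. SAP Section 3.4.2.2 uses the same term for the end of treatment: "Subjects who do not experience any of the competing events or the event of interest will be censored at the date of their last infusion". For the preceding infusion, SAP Section 3.6.3.4 uses other words: "Time relative to the most recent pegloticase infusion will be categorized as". On that usage the cut-off keeps washout samples from subjects who stopped early out of the Week 24 and Early Termination rows, a sensible purpose. Protocol Section 9.4.3.1.1 points the same way: "Activities related to pre/post infusion monitoring or medication dispensation will not be completed once a subject has stopped pegloticase infusions", and PK sampling is on its list. This stands. It confines the firm part of the point to Week 24, but does not rescue 17 days there, since a subject on continuous dosing can comply and still be excluded.

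A second reply is that a tolerance around a nominal 14-day sample is a legitimate choice, and a 20-day sample is not quite a 14-day trough. That would justify a limit on both sides. It does not justify keeping 8 days and dropping 18.

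Third, little is lost. The values leave only the summary and remain in the concentration listing with actual and planned times. The same rule applies to every infusion-duration group, so comparisons between groups need not be distorted. PK is exploratory, there is no inferential testing, and no primary or secondary endpoint uses these means. All of this stands and sets the weight of the point.

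**Conclusion.** The point holds for Week 24 under either reading: compliant samples at 18 to 20 days are excluded, compliant samples at 8 to 13 days are not, and the mean moves up if concentrations fall with time. It extends to Weeks 6, 12 and 20 only if *last infusion* means the preceding infusion.

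A reader might infer more: that on-schedule troughs are removed throughout the study and trough means are inflated by a known amount. The documents do not support that. The SAP's own usage favours the final-infusion reading, and Week 2 cannot exceed 17 days. The size rests on a half-life and a pattern of visit days that are assumed here. Across those assumptions the shift runs from 0.2% to about 10%. It is at most about 5.5% for half-lives of 7 days or more, and about 1% or less if most visits fall on target. The shares also assume independent deviations; sites that let a late visit carry forward would produce fewer long gaps. Low concentrations may have causes other than a long interval, such as antibodies.

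This is a minor, certain inconsistency between two rules, with an uncertain and probably small effect on exploratory PK summaries.

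**What to change.** In SAP Section 3.5.1:

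1. Replace 17 days with 20 calendar days. This keeps every in-window sample under either reading and stays below the 22-day minimum after a missed infusion.
2. State whether *last infusion* means the preceding or the final infusion. The choice matters beyond Week 24: under the final-infusion reading, a mid-course sample taken after a missed infusion but followed by another infusion is not excluded at any cut-off.
3. Report the number of concentrations excluded at each visit.

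The cost is one number, one definition and one line in a table, with no change to data collection or conduct. The small downside is a wider spread of sampling times in the summary, 8 to 20 days instead of 8 to 17. Early Termination visits do not follow the two-week grid, so a few such samples at 18 to 20 days would also come in; the per-visit counts and the existing listing leave them visible.
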